Clinical Study Protocol

Impact of ferric citrate vs ferrous sulfate on iron parameters and hemoglobin in individuals with moderate to severe chronic kidney disease (CKD) with iron deficiency

NCT02888171

Edition No.

06/14/18

1 Background and Rationale

Disturbances in iron homeostasis and bone/mineral metabolism are common complications of chronic kidney disease (CKD) that lead to a number of adverse outcomes including anemia, bone disease and cardiovascular mortality.¹ In clinical practice, disorders of iron homeostasis and bone/mineral metabolism are considered distinct entities and are treated separately. However, emerging evidence suggests that hormones regulating bone/mineral metabolism and iron homeostasis interact with each other on multiple levels, and that taking account of these interactions will improve the treatment of both disorders of iron homeostasis and disturbances in bone/mineral metabolism.

Iron plays a crucial role in the physiology of oxygen transport. Excess iron can lead to oxidative stress, while its deficiency can lead to anemia and poor oxygen delivery. Tight control of iron metabolism is required for normal physiological function. Since humans lack the ability to actively excrete excess iron, iron absorption is tightly controlled at the proximal small intestine and within the reticuloendothelial system.² Heparin is the master regulator of iron metabolism.³ Heparin regulates iron metabolism by binding to the cell-surface iron transporter, ferroportin, resulting in its internalization and lysosomal degradation.⁴ This effectively blocks iron absorption in the gut and iron release from macrophage and hepatocytes resulting in decreased iron availability for erythropoiesis.^{4,5} States of increased iron demand such as iron deficiency lead to a fall in heparin levels and thus increased iron absorption.^{3,6} Alternatively, in states of inflammation (such as CKD) or iron overload, heparin concentrations are elevated leading to decreased iron availability for erythropoiesis.^{3,6}

healthy volunteers, treatment with a single oral dose of ergocalciferol (100,000 IU) reduced hepcidin by 34% within 24 hours, which was sustained at 72 hours.¹⁷ Another study showed that nutritional vitamin D supplementation was associated with reduced hepcidin concentration in individuals with stage 3 or 4 CKD.¹⁸ Together, these data indicate that vitamin D is a potent inhibitor of hepcidin expression and increasing 1,25-dihydroxyvitamin D can lower hepcidin concentrations in individuals with CKD.

[figure not shown]
An important mechanism underlying the high prevalence of 1,25-dihydroxyvitamin D in CKD is elevated fibroblast growth factor 23 (FGF23) concentrations. FGF23 is a hormone secreted by bone cells that regulates vitamin D and phosphorus homeostasis.¹⁹ FGF23 enhances urinary phosphorus excretion and decreases the activation of vitamin D by inhibiting 1-alpha-hydroxylase, the enzyme which converts 25-hydroxyvitamin D to 1,25-dihydroxyvitamin D. Elevated circulating concentrations of FGF23 are extremely common in CKD, likely as a physiological adaptation to help maintain serum phosphorus in the normal range by enhancing urinary phosphorus excretion and reducing gut absorption of phosphorus via inactivation of vitamin D.¹⁹ While this is important for maintaining phosphorus balance in the short term, this has long-term consequences such as progressive reductions in the synthesis of 1,25-dihydroxyvitamin D.

Ferric citrate effectively binds dietary phosphorus while improving iron status and hemoglobin in individuals with CKD.²⁰ In addition, ferric citrate has been shown to reduce FGF23 concentrations in individuals with pre-dialysis CKD.²⁰ Based upon these data, we hypothesize that in individuals with moderate to severe CKD, as compared to standard oral iron formulations used to treat iron deficiency anemia, treatment with ferric citrate will more effectively improve iron parameters than ferrous sulfate, in part by mitigating the rise in hepcidin concentrations following iron repletion by reducing FGF23 concentrations and enhancing vitamin D activation. Thus, ferric citrate will be shown to be unique in that it can improve iron parameters and hemoglobin while at the same time mitigating iron-induced stimulation of hepcidin secretion, providing superior short- and long-term effects on iron-restricted erythropoiesis in CKD (**Figure 1**).

1.1 Study Rationale

Ferric citrate is an FDA-approved oral phosphorus binder that has been shown to be effective in reducing serum phosphorus and FGF23 concentrations and increasing iron stores and hemoglobin in individuals with non-dialysis-dependent CKD who have iron-deficiency anemia.²⁰ This may prove to be advantageous in individuals with pre-dialysis CKD who require iron supplementation for iron-deficiency anemia. This is because ferric citrate may not only restore iron stores in individuals who are iron deficient, but by lowering FGF23 concentrations, ferric citrate may increase local and systemic concentrations of 1,25-dihydroxyvitamin D, a powerful inhibitor of hepcidin synthesis, potentially attenuating the increase in hepcidin following oral iron supplementation. When compared to standard iron supplementation therapies (e.g., oral ferrous sulfate) that powerfully stimulate hepcidin secretion, this may then allow for greater iron bioavailability by increasing iron absorption in the gut while also reducing the degree of iron sequestration in RES stores. However, little is known about the comparative effectiveness of treatment with oral ferric citrate vs. oral ferrous sulfate (currently the standard of care) in increasing iron stores and hemoglobin in iron-deficient CKD patients. If ferric citrate is shown to not only improve overall iron status, but also partially mitigate the long-term effects of iron

Figure 1

supplementation on hepcidin secretion by increasing endogenously produced 1,25-dihydroxyvitamin D, this may indicate that ferric citrate can provide superior short- and long-term effects on iron-restricted erythropoiesis in CKD as compared to the current standard of care.

[figure not shown]
2 Study Objective and Hypotheses

The main objectives of the study are to compare the impact of ferric citrate compared to standard of care ferrous sulfate on serum iron, percent transferrin saturation (TSAT), ferritin, hemoglobin and hepcidin concentrations in individuals with moderate to severe CKD and absolute iron deficiency. We will test the following hypotheses:

Primary Hypothesis: In patients with moderate to severe CKD not requiring dialysis (estimated glomerular filtration rate 15-45 ml/min/1.73m²) with absolute iron deficiency (serum ferritin ≤300ng/ml and TSAT ≤ 30%), treatment with ferric citrate will lead to greater improvements in markers of iron bioavailability (serum iron, ferritin, transferrin saturation) than treatment with ferrous sulfate.

Secondary Hypotheses: In patients with moderate to severe CKD not requiring dialysis (estimated glomerular filtration rate 15-45 ml/min/1.73m²) with absolute iron deficiency (serum ferritin ≤300ng/ml and TSAT ≤ 30%), as compared to treatment with ferrous sulfate for 12 weeks, treatment with ferric citrate for twelve weeks will result in (1) a greater rise in hemoglobin concentrations and (2) a lower rise in serum hepcidin concentrations.

3 Investigational Plan (Figure)

3.1 General overview

- Randomized, open-label study of ferric citrate vs. ferrous sulfate in patients with moderate to severe CKD (eGFR 15 – 45 ml/min/1.73m²).
- Participants will be recruited from the outpatient nephrology clinics at the University of Alabama at Birmingham (UAB).
- Written informed consent will be obtained at the screening visit after the study has been explained in full.
- Participants taking oral iron supplements at the time of the screening visit will undergo a four week wash-out period prior to beginning study medications.
- After eligibility is confirmed following the screening visit (and wash-out period if necessary), participants will be randomly assigned 1:1 to take ferric citrate at a dose of 2 grams three times a day with meals (n=30) or ferrous sulfate at a dose of 325 mg by mouth three times a day between meals (n=30) for a total of twelve weeks.
- Fasting blood and urine samples will be collected at baseline and two, six and 12 weeks after baseline for measurement of study outcome variables. Data for the outcome variables as well as safety will be collected at these time points.
- The study will end at 12 weeks, a final blood and urine sample will be drawn and intervention will be stopped.

3.2 Study Population

3.2.1 Participant Recruitment

Participants will be recruited via several different methods:

- Outpatient clinic visits: Study staff will pre-screen patients coming in for their scheduled appointments at the Kirklin Clinic (TKC), the major outpatient nephrology clinic at UAB.
- Advertisements: Advertisements will be posted in local newspapers and online resources to recruit individuals with a history of kidney disease from the city of Birmingham and surrounding communities. Study flyers will be posted around the UAB hospital and outpatient clinic locations. These strategies have been successful in recruiting participants with CKD in randomized, controlled studies of CKD patients at our center.

3.2.2 Inclusion Criteria

- 18 years of age or older
- Moderate to severe kidney disease not requiring renal replacement therapy (eGFR 15-45 ml/min/1.73m² as determined by the CKD-EPI formula).
- Absolute iron deficiency as defined as a transferrin saturation \leq 30% and a ferritin \leq 300 ng/ml.

3.2.3 Exclusion Criteria

- Hemoglobin concentrations $>$ 13 g/dL
- Severe anemia defined as a hemoglobin $<$ 8.0 g/dL for males or a hemoglobin $<$ 7.0 g/dL for females.
- Known disorder of iron homeostasis (e.g., hemochromatosis)
- Known gastrointestinal disorder (irritable bowel disease, inflammatory bowel disease)
- Known or biochemical evidence of liver disease (ALT/AST or bilirubin $>$ 3x normal)
- Serum phosphorus concentrations $<$ 3.0 mg/dL
- Any known cause of anemia other than iron deficiency or CKD (e.g., sickle cell anemia)
- Symptomatic gastrointestinal bleeding within 12 weeks prior to the screening visit.
- Subjects receiving any form of renal replacement therapy including hemodialysis, peritoneal dialysis, or renal transplant.
- Pregnancy or lactation in female participants
- Life expectancy less than 6 months
- Receipt of erythropoiesis stimulating agents within 4 weeks of screening.
- Receipt of intravenous iron therapy within 8 weeks of screening.
- Blood transfusion within 4 weeks of screening
- Known allergies or severe adverse reactions to previous oral iron therapy
- Current use of oral phosphorus binders
- Current use of an active vitamin D analog
- Concomitant participant in another clinical study with investigational medicinal products.

3.2.4 Concurrent use of oral iron supplements

Potential participants taking oral iron (either as an over-the-counter supplement or prescribed medication) will not be excluded but will be required to stop the iron for at least 4 weeks prior to entering the study.

3.2.4.1 Concurrent use of other medications

All concurrent medications will be recorded in study participants. If participants are taking oral calcium supplements or nutritional vitamin D analog, they will be allowed to continue to take them as long as the dose does not change during the course of the study.

3.3 Justification of selection criteria

The selection criteria were chosen to focus enrollment on individuals with moderate to severe CKD (eGFR 15 – 45 ml/min/1.73m²) who are iron deficient and (1) would not be exposed to particular risks from the study drug and (2) would not have conditions that would impact the aims of the study. The reason why we chose this cut-off for eGFR is that we wanted to enroll individuals who would benefit the most from an intervention that not only provided supplemental iron but also could potentially help to attenuate the rise in hepcidin following iron supplementation by reducing FGF23 concentrations. While it is possible that CKD patients with a higher eGFR would also benefit from using ferric citrate to increase iron stores, these individuals would likely have milder forms of iron deficiency and/or mildly increased FGF23 concentrations, making it more difficult to ascertain whether a therapy that combined iron repletion with phosphorus lowering would more effectively improve iron bioavailability than individuals with more severe forms of kidney disease. We chose not to include individuals with an eGFR < 15 ml/min/1.73m² because in our experience, it would be very challenging to find individuals at this low an eGFR who would be eligible for enrollment given our exclusion criteria—particularly avoidance of ESA exposure—within the period of time for recruitment proposed for this study (2 years). Furthermore, these individuals are more likely to be hospitalized and/or progress to ESRD requiring dialysis, which would increase the drop-out rate and require us to either extend the recruitment period or enroll a larger sample size than currently planned.

3.4 Study Schedule (Figure 2)

3.4.1 Screening Visit

Written, informed consent will be obtained by study staff during the screening visit after the study has been explained in full. Participants will be instructed to come to the screening visit after at least an 8-hour fast. Participants who provide consent will have height and weight obtained. Age, gender and race/ethnicity data will be recorded. Blood samples will be drawn to measure screening labs to ensure eligibility. In addition, female subjects of child-bearing age (\leq 55 years) will have a rapid urine test for beta-HCG performed to rule out pregnancy. Eligibility to continue with the study will be determined after review of screening tests. If any screening laboratory values are found to disqualify the participant, he or she will be informed of the findings, and will be asked to follow-up with his or her primary care physician or nephrologist for further evaluation if necessary (e.g., for a very low hemoglobin level).

Participants found not to be eligible following the screening visit and lab testing will be allowed to re-screen at a later time provided that the major reason for screening failure can be reasonably expected to be resolved within six months of the original screening visit (for example, a CKD patient who received IV iron three weeks ago, but who will refrain from IV iron within the next six months may be eligible for re-screening at a later date).

3.4.2 Washout Period

Participants who are currently receiving oral iron ferrous sulfate (or other oral iron preparations) will undergo washout of these medications for four weeks.

3.4.3 Visit 1 (Day zero)

After eligibility is confirmed in the screening visit and following the washout period if necessary, participants will come to the UAB Clinical Research Unit (CRU) in the morning after an overnight fast for visit 1 (Day 0). During this visit, participants will undergo fasting blood collection to

establish baseline measurements for primary outcome variables (iron, TIBC, ferritin), secondary outcome variables (hemoglobin, hepcidin, FGF23) and safety measures (eGFR, calcium, phosphorus). At this time subjects will also be randomly assigned to a treatment arm (ferric citrate vs. ferrous sulfate).

3.4.3.1 Randomization (Visit 1)

All eligible participants will be randomized by the research pharmacist in a 1:1 fashion into one of two treatment arms:

- Ferrous sulfate at a dose of 325 mg by mouth three times a day between meals
- Ferric citrate at a dose of 2 grams three times a day with meals

3.4.4 Visit 2 (week 2)

- Participants will come to the UAB CRU, where participants will undergo vital sign measurement and fasting blood collection for measurement of study outcome variables and safety measures.
- Pills remaining in the study medication bottles of each participant will be counted to ensure compliance and accountability for discrepancies in study drug use will be performed.
- Participants will be asked questions about intercurrent medical events and changes in clinical condition from the last visit. Events that meet the definition of an adverse event (see section 3.9.2) will be documented.

3.4.5 Visit 3 (week 6)

- Participants will come to the UAB CRU, where participants will undergo vital sign measurement and fasting blood collection for measurement of study outcome variables and safety measures.
- Pills remaining in the study medication bottles of each participant will be counted to ensure compliance and accountability for discrepancies in study drug use will be performed.
- Participants will be asked questions about intercurrent medical events and changes in clinical condition from the last visit. Events that meet the definition of an adverse event (see section 3.9.2) will be documented.

3.4.6 Visit 4 (week 12)

- Participants will come to the UAB CRU, where participants will undergo vital sign measurement and fasting blood collection for measurement of study outcome variables and safety measures.
- Pills remaining in the study medication bottles of each participant will be counted to ensure compliance and accountability for discrepancies in study drug use will be performed.
- Participants will be asked questions about intercurrent medical events and changes in clinical condition from the last visit. Events that meet the definition of an adverse event (see section 3.9.2) will be documented. At the end of this visit, the study will be completed.

3.5 Study Drug Dispensing and Logistics

3.5.1 Study drug dispensing

The UAB research pharmacy will be responsible for storage of all study drugs in a secure facility. They will also be responsible for procurement of ferrous sulfate from commercial

sources (ferric citrate will be shipped to the research pharmacy from the study sponsor). The research pharmacy will also be responsible for participant randomization and dispensation of study drug in appropriately marked containers. Written instructions on how study drugs are to be taken will be provided to all participants, and will be reinforced by face-to-face contact with study staff at the baseline and all follow-up visits.

3.6 Compliance assessment

Study drug will be provided to participants at the baseline visit (visit 1), visit 2 and visit 3. Study staff will maintain a study drug dispensing log to document drug dispensing during the entire study. Participants will be instructed to return the study drug bottles including unused study drug at each follow-up visit. Any discrepancies between the remaining study drug in the bottles and the number that should be remaining will be discussed with the study participants at the time of the visits and an explanation must be documented. Participants will also be required to inform study personnel of intentional or inadvertent failure to take a study drug according to the written schedule between study visits.

3.7 Protocol for Handling of Withdrawals

3.7.1 Discontinuation of the study drug

Participants who discontinue the study drug will be expected to continue in the follow-up period and complete all study-specific visits. If a participant is unable to attend a follow-up study visit, contact by telephone is permitted to determine the reason why they are not able to attend a follow-up study visit and determine whether these assessments can be rescheduled.

The study drug can be discontinued if:

- The participant becomes pregnant
- Any investigational drug other than the study drug is used
- Any suspected drug-related adverse events or serious adverse events occur
- If any of the exclusion criteria apply during treatment (e.g., receipt of kidney transplant)
- A significant violation of the study protocol occurs.

Importantly, study drugs can be temporarily discontinued for reasons as outlined in section 3.9.1.1 below.

3.7.2 Discontinuation from the study

Participants can be withdrawn from the study at any time if they specifically ask to withdraw or if, in the opinion of the study PI, continuation of the study would be harmful to the participant. In addition, a participant can be withdrawn at any time by the PI if he or she repeatedly violates study protocol.

Participants withdrawn prior to the final scheduled visit will be asked to attend a close-out visit in which they provide blood and urine samples (for final analyses), and complete documentation related to the development of any adverse events.

If the withdrawal is due to an adverse event, participants will be followed until the event resolves or it is shown that the adverse event was not due to the study medication.

Randomized participants who withdraw prematurely will not be replaced. A participant who withdraws after signing informed consent but before randomization can be replaced.

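### Section 3.7.2 lets the investigator in an open-label trial end follow-up for repeated protocol violation, so week-12 TSAT and ferritin may be missing or replaced by an earlier sample

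*Combined protocol and SAP*

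**What the plan says.** Two sections deal with a participant who breaks the protocol.

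- Section 3.7.1 (Discontinuation of the study drug) includes this among the grounds on which drug can be stopped: "A significant violation of the study protocol occurs". It also says: "Participants who discontinue the study drug will be expected to continue in the follow-up period and complete all study-specific visits".
- Section 3.7.2 (Discontinuation from the study) first allows withdrawal at the participant's request, or where the investigator thinks continuing would be harmful. It then adds that "a participant can be withdrawn at any time by the PI if he or she repeatedly violates study protocol".

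Neither *significant* nor *repeatedly* is defined, and nothing says which section governs when the same conduct fits both.

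For people who leave the study, 3.7.2 provides: "Participants withdrawn prior to the final scheduled visit will be asked to attend a close-out visit in which they provide blood and urine samples". Those samples are described as being for the final analyses, but the timing of the visit is not given. Randomised participants who withdraw are not replaced.

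Three other places matter. Section 3.1 describes a "Randomized, open-label study of ferric citrate vs. ferrous sulfate". Section 3.6 says of pill counts that "Any discrepancies between the remaining study drug in the bottles and the number that should be remaining" are to be discussed with the participant and an explanation documented; it sets no adherence threshold. Section 4.3 invokes intention to treat, admits to the efficacy analysis anyone with one dose and one assessment after baseline, and fits a repeated-measures mixed model. It does not say how an off-schedule close-out sample enters that model.

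**The concern.** Whether a randomised participant is followed to week 12 should not depend on the choice of someone who knows the arm. Under 3.7.2 it can. The ground is conduct after randomisation, not safety and not the participant's own wish, so nothing in that ground calls for blood draws to stop.

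The primary outcomes in Section 4.1 are TSAT and ferritin, which respond directly to how much iron is taken. If the violations that lead to removal include missed doses, the people removed would tend to be those with the smaller rise. The regimens differ in their relation to meals (Section 3.4.3.1), so equal adherence in the two arms cannot be assumed. An arm that lost more such people would look better than it is. An early close-out value treated as the endpoint would be a different problem: it would record less than 12 weeks of treatment as if it were 12.

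**Working it through.** The plan gives no figure on this point, so there is none to reproduce. The check has a textual part and an illustrative calculation.

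**1. The two rules side by side**

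| | Section 3.7.1 | Section 3.7.2 |
|---|---|---|
| Trigger | significant violation | repeated violation |
| Force | permissive | permissive |
| What ends | study drug | study participation |
| Week-12 sample | expected | not scheduled; a close-out visit is requested |

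A violation can be both significant and repeated. The same participant can then be followed to week 12 or not, and either course complies with the protocol.

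**2. Which measurements are at risk**

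Pill counts take place at weeks 2, 6 and 12, at the same visits as the blood draws (Sections 3.4.4 to 3.4.6). If repetition is judged from pill counts, a second discrepant count cannot exist before week 6. By then the week-2 and week-6 draws have fallen due, and only week 12 is exposed. Earlier removal would need other evidence, such as the self-report between visits that 3.6 requires. Someone removed before week 2 who did not attend close-out would have no assessment after baseline and would leave the efficacy analysis altogether.

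**3. An upper bound for ferritin**

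Inputs from Section 4.4: 30 per arm; a ferritin rise of 77.5 in the prior study; a target difference of 20%, which is 0.20 × 77.5 = 15.5.

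Assumptions, none of them in the documents: *k* of 30 are removed, all from one arm; they would have had no rise; the other participants rise by 77.5; no data from those removed are used.

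Mean of all randomised = 77.5 × (30 − *k*)/30. Mean of completers = 77.5. Overstatement = 77.5 × *k*/30.

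- *k* = 1: 77.5 − 74.92 = 2.58, about 2.6; 2.58/15.5 = 17% of the target.
- *k* = 3: 77.5 − 69.75 = 7.75; 7.75/15.5 = 50% of the target.

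**4. How far the bound depends on its assumptions**

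- If those removed had half the rise, the overstatement is halved: 1.29 for *k* = 1 (8% of target) and 3.88 for *k* = 3 (25%).
- If *k* are removed from each arm, all with no rise, and the ferrous sulfate completers rise by 77.5 − 15.5 = 62.0, the difference between arms is overstated by 15.5 × *k*/30: 0.52 for *k* = 1 (3%) and 1.55 for *k* = 3 (10%).
- The figure of 77.5 is a difference from placebo. Using it as one arm's own rise sets the scale only.
- The planned mixed model keeps the early values, which lowers all these figures by an amount that the documents do not allow one to compute.

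**The case against.** The strongest reply has four parts.

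*The sections do not conflict.* The triggers differ and both clauses are permissive, so they could be a graduated response: stop drug first, end participation later. This stands in part. A reader might infer a flat contradiction, or that 3.7.1 confines every violation to stopping drug; the text says neither. What remains is an undefined overlap.

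*The documents do not mention non-adherence as a ground for withdrawal.* Section 3.7.2 speaks of protocol violations, and 3.6 answers a pill-count discrepancy with a discussion and a documented explanation. This also stands: the link to missed doses is an inference. It is a reasonable one, because 3.6 has adherence checked at every follow-up visit and requires participants to report doses not taken as instructed.

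*The data are not lost.* A close-out sample is requested, and earlier values stay in the model. This reduces the problem without removing it. Attendance is only requested, the sample would come before the scheduled week-12 visit, and 4.3 does not say how it is used. A reader might infer that the week-12 outcomes of poor adherers are lost, or that the close-out sample is drawn on the day of leaving. The documents support only that week-12 values may be missing or displaced, and they do not date the close-out visit.

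*Losses from poor tolerability arise elsewhere.* Section 3.9.1.1 has its own rule for persistent gastrointestinal upset. That is correct; this point does not concern that rule and the fix leaves it unchanged.

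**Conclusion.** The point holds as a weakness of design in follow-up. Applying 3.7.2 as written can remove or displace week-12 TSAT and ferritin after randomisation, at the discretion of an investigator in an open-label trial, on a ground that could relate to adherence and to arm. That fits poorly with the intention-to-treat principle in 4.3, and it goes beyond a missing definition.

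The likely size is small. The range of 2.6 to 7.75 ng/mL (17% to 50% of the 15.5 target) is an upper bound. It rests on 1 to 3 removals confined to one arm, no rise in those removed, a placebo-compared figure used as an arm's own rise, and a completers' mean that the plan does not use. A reader might take it as the expected bias; it should not be read that way. The documents give no expected number of such withdrawals. The case for the change is that it is cheap and removes an avoidable source of selection.

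**What to change.** 1. In Section 3.7.2, remove repeated protocol violation as a ground for ending study follow-up. State that such participants are still asked to attend the remaining scheduled visits and blood draws, unless they withdraw consent or continuing would be harmful. Both of those grounds are already in 3.7.2 and stay.
2. Leave the decision on study drug where it is, as a separate matter under 3.7.1. This point proposes no change to when drug is stopped.
3. In Section 4.3, state that a close-out sample is analysed at its actual time since baseline and is not treated as the week-12 value. If time is fitted as scheduled visits, say how an off-schedule sample is placed.

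The cost is one protocol amendment and a few visits with poorly adherent participants. Section 3.7.1 already expects follow-up of people who have stopped drug, so this extends an existing rule and adds no new procedure.
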